#### **4.2. Exclusion Criteria**

Any potential subject who meets any of the following criteria will be excluded from participating in the study:

1. Criterion modified per Amendment 2
  - 1.1. Has a history of, or current signs and symptoms of, severe renal insufficiency (creatinine clearance <30 mL/min); moderate to severe hepatic insufficiency (Child-Pugh Score  $\geq 7$ ), significant or unstable cardiovascular, respiratory, gastrointestinal, neurologic (including narcolepsy), hematologic, rheumatologic, immunologic or endocrine disorders (including uncontrolled hypo- or hyperthyroidism or diabetes, or insulin-dependent diabetes mellitus). Subjects with non-insulin dependent diabetes mellitus who are well-controlled (hemoglobin A1c [HbA1c]  $\leq 7.5\%$  and fasting glucose  $\leq 126$  mg/dL at screening) may be eligible to participate if otherwise medically healthy, and if on a stable regimen of glucose-lowering medications for at

- least 2 months prior to screening.
2. Has a fasting triglyceride concentration  $\geq 500$  mg/dL at screening.
  3. Has Cushing's Disease, Addison's Disease, primary amenorrhea, or other evidence of significant medical disorders of the HPA axis.
  4. Has a current or recent history of serious suicidal ideation within the past 6 months, corresponding to a positive response on item 4 (active suicidal ideation with some intent to act, without specific plan) or item 5 (active suicidal ideation with specific plan and intent) for ideation on the C-SSRS, or a history of suicidal behavior within the past year, as validated by the C-SSRS at screening or Day 1. Subjects with a prior suicide attempt of any sort, or prior serious suicidal ideation/plan within the past 6 months, should be carefully screened for current suicidal ideation and only subjects with non-serious items (1-3 of the suicidal ideation section of the C-SSRS) may be included at the discretion of the investigator.
  5. Has had clinically significant acute illness within 7 days before the first dose of study drug.
  6. Has a history of epilepsy, NMS or Tardive Dyskinesia.
  7. Has a history of previous non-response to an adequate trial of quetiapine as an adjunctive treatment for MDD (adequate trial defined as  $\geq 150$  mg for 4 weeks or more).
  8. Criterion modified per Amendment 2
    - 8.1. Has a history of lack of response to 3 or more adequate antidepressant treatments, as indicated by no or minimal ( $\leq 25\%$  improvement in symptoms) when treated with an antidepressant of adequate dose (per MGH-ATRQ) and duration (at least 4 weeks).
  9. Has a history or evidence of noncompliance with current antidepressant therapy.
  10. Has taken a known moderate or strong inhibitor/inducer of CYP3A4 and CYP2C9 or a dual inhibitor/inducer of CYP3A4 and CYP2C9 within 14 days (or after washout ie, duration of 5 times the drug's half-life) before the first study drug administration on Day 1 until the follow-up visit. See [Attachment 1](#) for examples of strong inhibitor or inducer of CYP3A4 and CYP2C9 or a dual inhibitor of CYP3A4 and CYP2C9. Fluvoxamine is a moderate CYP2C9 inhibitor and a mild CYP3A inhibitor, and will not be excluded from the study.
  11. Has a primary DSM-5 diagnosis of panic disorder, generalized anxiety disorder, social anxiety disorder, or specific phobia which has been the primary focus of psychiatric treatment within the past 2 years. These are allowed as secondary diagnoses as long as

MDD is the primary focus of treatment according to the investigator.

12. Current active DSM-5 diagnosis of obsessive-compulsive disorder, posttraumatic stress disorder, anorexia nervosa, or bulimia nervosa is exclusionary. These disorders need for be in remission for at least 1 year for the subject to be enrolled.
13. Has history or current diagnosis of a psychotic disorder, bipolar disorder, intellectual disability, autism spectrum disorder, borderline personality disorder, somatoform disorders, or fibromyalgia.
14. Has any significant primary sleep disorder, including but not limited to obstructive sleep apnea, restless leg syndrome, narcolepsy or parasomnias.
15. Has significant hypersomnia that is not related to insomnia disorder or MDD (based on clinical judgment of the investigator).
16. Has a history of a bariatric surgical procedure within 3 years before the screening visit.
17. Has a known malignancy or history of malignancy within 5 years before screening (exceptions are squamous and basal cell carcinomas of the skin and carcinoma in situ of the cervix, or malignancy that in the opinion of the investigator, with concurrence with the sponsor's medical monitor, is considered cured with minimal risk of recurrence).
18. Has clinically significant ECG abnormalities at screening or Day 1 prior to randomization defined as:
  - QT interval corrected according to Fridericia's formula (QTcF):  $\geq 450$  msec (males);  $\geq 470$  msec (females)
  - Evidence of 2nd and 3rd degree atrioventricular block, or 1st degree atrioventricular block with PR interval  $> 200$  msec, left bundle branch block (LBBB).
  - Features of new ischemia
  - Other clinically important arrhythmia.
19. Criterion modified per Amendment 1

Note: Subjects with right bundle branch block (RBBB) may be allowed provided confirmation that RBBB is not associated with underlying cardiac/lung diseases.

- 19.1. Has received any prior treatment with electroconvulsive therapy, vagal nerve stimulation, or a deep brain stimulation device. Has received ketamine or esketamine for the treatment of depression.

20. Ongoing psychological treatments (eg, Cognitive Behavior Therapy, Interpersonal Psychotherapy, Psychodynamic Psychotherapy, etc.), initiated within 2 months prior to start of the double-blind treatment phase. A subject who has been receiving ongoing psychological treatment for a period of greater than 2 months is eligible, if the investigator deems the psychological treatment to be of stable duration and frequency.
21. Has a history of substance or alcohol use disorder according to DSM-5 criteria within 6 months before screening or positive test result(s) for alcohol and/or drugs of abuse (opiates [including methadone], cocaine, amphetamines, methamphetamines, cannabinoids, barbiturates, 3,4-Methylenedioxymethamphetamine [XTC] and benzodiazepines) at screening.
22. Has known allergies, hypersensitivity, or intolerance or any contraindication to JNJ-42847922, quetiapine XR, or their excipients (refer to Investigator's Brochure for JNJ-42847922 and Summary of Product Characteristics [SmPC]/Package Insert [PI] for quetiapine XR).
23. Has either donated 1 or more units (approximately 450 mL) of blood or acutely lost an equivalent amount of blood within 60 days before the first dose of study drug.
24. Has cognitive impairment that would render the informed consent invalid, or limit the ability of the subject to comply with the study requirements.
25. Has any condition for which, in the opinion of the investigator, participation would not be in the best interest of the subject (eg, compromise the well-being) or that could prevent, limit, or confound the protocol-specified assessments.
26. Has taken any disallowed therapies as noted in Section 8 Prestudy and Concomitant Therapy before the planned first dose of study drug.
27. Has received an investigational drug (including investigational vaccines) or used an invasive investigational medical device within 3 months before the planned first dose of study drug or is currently enrolled in an investigational study.
28. Criterion modified per Amendment 2
  - 28.1 Is pregnant or breastfeeding while enrolled in this study or within 1 month after the last dose of study drug.
29. Plans to father a child while enrolled in this study or within 3 months after the last dose of study drug.
30. Has had major surgery (eg, requiring general anesthesia) within 2 weeks before screening, or will not have fully recovered from surgery, or has surgery planned

during the time the subject is expected to participate in the study.

Note: Subjects with planned surgical procedures to be conducted under local anesthesia may participate.

31. Is an employee of the investigator or study center, with direct involvement in the proposed study or other studies under the direction of that investigator or study center, as well as family members of the employees or the investigator.

**NOTE:** Investigators should ensure that all study enrollment criteria have been met at screening. If a subject's clinical status changes (including any available laboratory results or receipt of additional medical records) after screening but before the first dose of study drug is given such that he or she no longer meets all eligibility criteria, then the subject should be excluded from participation in the study. Section 17.4, Source Documentation, describes the required documentation to support meeting the enrollment criteria.

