#### 4. SUBJECT POPULATION

Screening for eligible subjects will be performed within 4 weeks before administration of the study drug.

The inclusion and exclusion criteria for enrolling subjects in this study are described in the following 2 subsections. If there is a question about the inclusion or exclusion criteria below, the investigator must consult with the appropriate sponsor representative and resolve any issues before enrolling a subject in the study. Waivers are not allowed. Exceptional and limited retesting of abnormal screening values (particularly, if the initial laboratory testing was not done under fasting conditions) that would otherwise lead to exclusion may be allowed after discussion and approval by the sponsor during the screening phase (to reassess eligibility). This should only be considered if there is no anticipated impact on subject safety.

For a discussion of the statistical considerations of subject selection, refer to Section 11.2, Sample Size Determination.

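### Exclusion 4 bars serious suicidal ideation in the past 6 months, then appears to let investigators admit the same subjects if current ideation is only C-SSRS items 1 to 3

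*Protocol*

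**What the plan says.** Sentence 1 of exclusion 4 (Protocol Section 4.2) begins "Has a current or recent history of serious suicidal ideation within the past 6 months, corresponding to a positive response on item 4" and goes on to add item 5. It also excludes suicidal behavior in the past year, and it refers to the C-SSRS at screening or Day 1.

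Sentence 2 addresses subjects with a suicide attempt of any kind, or "prior serious suicidal ideation/plan within the past 6 months, should be carefully screened for current suicidal ideation and only subjects with non-serious items", which it identifies as items 1 to 3. Those subjects "may be included at the discretion of the investigator".

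Three other provisions bear on how the two sentences fit together:

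- The lead-in to Section 4.2: "Any potential subject who meets any of the following criteria will be excluded from participating in the study".
- Section 4: "Waivers are not allowed". It also says: "If there is a question about the inclusion or exclusion criteria below, the investigator must consult with the appropriate sponsor representative" and settle the matter before enrolment.
- Section 1.4 lists keeping high-risk subjects out, with a pointer to Section 4.2, among the measures against suicidality.

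The current text marks criteria changed by an amendment. Exclusion 4 carries no such mark.

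**The concern.** The two sentences appear to describe the same people over the same 6 months and to dispose of them differently: one excludes, the other leaves it to the investigator. Nothing in the criterion says which governs. Two sites could each believe they are following the protocol and still decide differently on identical patients.

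What is at stake is a safety control that Section 1.4 relies on by name. A site that treats sentence 2 as an exception could enrol people with recent serious ideation whom sentence 1 is meant to keep out. There is also a small reporting effect. SAP Section 4.5 plans a count of subjects in the safety set who fail each criterion, and for exclusion 4 that count depends on which sentence a site applied.

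**Working it through.** No arithmetic applies, and the plan gives no figure to reproduce. The check sets the two sentences side by side.

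**Step 1: what serious means.** Sentence 1 ties it to item 4 (some intent, no specific plan) or item 5 (plan and intent). Sentence 2 names no items for the past ideation, but it contrasts serious with non-serious items 1 to 3. The natural reading is therefore items 4 and 5 in both sentences.

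**Step 2: the windows.** For ideation both sentences use 6 months. For attempts, sentence 1 looks back 1 year over suicidal behavior, while sentence 2 sets no limit.

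**Step 3: test cases.** Each row assumes that nothing else in the history is disqualifying.

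| Subject | Sentence 1 | Sentence 2 |
|---|---|---|
| Item 4 or 5 now | Excluded | No permission |
| Item 4 or 5 three months ago, items 1 to 3 now | Excluded | May be included |
| Item 4 or 5 more than 6 months ago, items 1 to 3 now | Not excluded | Ideation part does not apply |
| Attempt within the past year, items 1 to 3 now | Excluded | May be included |
| Attempt more than 1 year ago, items 1 to 3 now | Not excluded | May be included |

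Rows 2 and 4 conflict. Row 5 shows that the attempt part of sentence 2 has a coherent use outside sentence 1's look-back. The ideation part has no such use on the reading in step 1.

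**Step 4: can a site comply with both?** In rows 2 and 4 sentence 1 allows one action, exclude. Sentence 2 is a permission and allows two, include or exclude. The only action common to both is exclude.

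**Step 5: how nearby criteria are drafted.**

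- Exclusion 1.1 bars uncontrolled or insulin-dependent diabetes and then permits a different group: "Subjects with non-insulin dependent diabetes mellitus who are well-controlled".
- Exclusion 20 bars psychological treatment started within 2 months and uses the complementary window: "A subject who has been receiving ongoing psychological treatment for a period of greater than 2 months is eligible".
- Exclusion 17 does permit some malignancies inside its own 5-year window, but it labels them exceptions.

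In these three criteria the permitted group either lies outside the excluded one or is called an exception. Exclusion 4 does neither.

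**The case against.** The strongest reply is that the protocol already supplies the rule. Meeting any criterion means exclusion, waivers are ruled out, and questions go to the sponsor before enrolment. Sentence 2 is worded restrictively and sits inside an exclusion, so it can be read as an extra screen. Step 4 confirms that a site which excludes is always compliant.

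That much stands, but it does not remove the ambiguity. A site acting on a permission written into the criterion would not think it was granting a waiver. The duty to consult arises only when the site sees a question, and sentence 2 hands the decision to the investigator.

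A second reply concerns step 1. Sentence 2 speaks of ideation or a plan and assigns no item numbers to the history. A recent plan reported without intent, or a history not rated 4 or 5, might fall under sentence 2 but outside sentence 1. So a reader might infer that, once sentence 1 is enforced, the ideation part of sentence 2 can admit nobody. The documents do not establish that: equating serious ideation or plan with items 4 and 5 is the better reading, but not the only one.

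A third reply is that other protections remain. Exclusion 25 allows exclusion in the subject's interest, the C-SSRS is scheduled at every clinic visit, and Section 10.2 stops treatment for safety reasons or for acute ideation with a clear plan. These limit the harm, but they do not settle who should be enrolled.

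**Conclusion.** Exclusion 4 is internally inconsistent and should be corrected. On the natural reading, sentence 2 gives discretion over subjects excluded by sentence 1: those with item 4 or 5 ideation in the past 6 months whose current ideation is limited to items 1 to 3, and similarly those with an attempt in the past year. This weakens the mitigation that Section 1.4 relies on.

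The conclusion rests on reading serious as items 4 and 5 in both sentences. The documents do not say how many screened or randomized subjects fall in the overlap, so no count can be given.

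A reader might go further and infer that the protocol admits people with current serious ideation, or that the trial's comparison is compromised. Neither is supported. Current item 4 or 5 ideation is excluded by sentence 1 and gets no permission from sentence 2, and sample size, power and the primary analysis do not depend on this wording. Nor do the documents show that any site has enrolled a subject under sentence 2. Inconsistent handling is a possibility that the text leaves open.

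**What to change.** Keep the careful-screening instruction and make sentence 1 prevail. Sentence 2 could become:

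> Where a subject has ever attempted suicide or had suicidal ideation or a plan, and is not excluded by the 6-month (item 4 or 5) or 1-year (behavior) look-back above, screen carefully for ideation now. The investigator may include the subject only if current ideation is absent or limited to items 1 to 3.

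This still covers recent ideation or plans not rated 4 or 5, which deleting the sentence would leave without the screening instruction.

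The documents do not state the intent, so the sponsor should first confirm that the look-backs were meant to be absolute and then send sites a clarification. If an exception was intended, it should be labelled as one and reconciled with Section 1.4.

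The cost is a short amendment with IEC/IRB submission, a site communication, and possibly a few fewer eligible subjects. SAP Section 4.5 needs no retroactive rule: while the intent is unconfirmed, subjects enrolled under an express permission should not be reclassified as failing exclusion 4.

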#### **4.3. Prohibitions and Restrictions**

Potential subjects must be willing and able to adhere to the following prohibitions and restrictions during the course of the study to be eligible for participation:

1. Refer to Section 8, Prestudy and Concomitant Therapy for details regarding prohibited and restricted therapy during the study.
2. Agree to follow all requirements that must be met during the study as noted in the Inclusion and Exclusion Criteria (eg, contraceptive requirements).
3. The use of limited amounts of alcohol (up to 2 units daily eg, one pint of ordinary strength beer, lager or cider [3% to 4% alcohol by volume]; or a pub measure [50 mL] of spirits (40% alcohol by volume); or 2 standard pub measure [100 mL] of fortified wine [20% alcohol by volume]) will be allowed during the study, with the exception of the evenings before study visits and 12 hours before salivary cortisol sample collections.
4. Strenuous exercise may affect study specified assessments and safety laboratory results; for this reason, strenuous exercise should be avoided within 24 hours before all planned study visits
5. Biomarker blood samples are to be collected under fasting conditions ( $\geq 8$  hrs, water permitted); for saliva samples, no food or drink (water permitted)  $\geq 1$  hour prior to collection.
6. Subjects will be advised not to donate blood during the study and for at least 3 months after completion of the study.

7. Subjects should be cautioned not to drive a car or operate machinery or engage in any potentially hazardous activities if they have had less than a full night's sleep (6-8 hours) following administration of the study drug or at any time during the study if the subject feels that his or her baseline capacity is impaired.

Note: At any point during the study, if subjects manifest significant next-day sleepiness, they are advised to inform the investigator. Such subjects may be discontinued or advised not to drive or operate machinery.

## **5. TREATMENT ALLOCATION AND BLINDING**

### **Treatment Allocation**

#### ***Procedures for Randomization and Stratification***

Central randomization will be implemented in this study. Subjects will be randomly assigned to 1 of 2 treatment groups based on a computer-generated randomization schedule prepared before the study by or under the supervision of the sponsor. The randomization will be balanced by using randomly permuted blocks and will be stratified by insomnia status (significant insomnia symptoms [ISI score  $\geq 15$ ] at baseline versus no significant insomnia symptoms [ISI score  $< 15$ ] at baseline).

The interactive web response system (IWRS) will assign a unique treatment code, which will dictate the treatment assignment and matching study drug kit for the subject. The requestor must use his or her own user identification and personal identification number when contacting the IWRS, and will then give the relevant subject details to uniquely identify the subject.

### **Blinding**

To maintain the study blind, the study drug container will have a label containing the study name, study drug number, and reference number. The label will not identify the study drug in the container. However, if it is necessary for a subject's safety, the study blind may be broken and the identity of the study drug ascertained. The study drug number will be entered in the case report form (CRF) when the study drug is dispensed. The study drugs will be identical in appearance and will be packaged in identical containers.

The investigator will not be provided with randomization codes. The codes will be maintained within the IWRS, which has the functionality to allow the investigator to break the blind for an individual subject.

Data that may potentially unblind the treatment assignment (ie, study drug concentrations, study drug preparation/accountability data, treatment allocation, and biomarker or other specific laboratory data) will be handled with special care to ensure that the integrity of the blind is maintained and the potential for bias is minimized. This can include making special provisions, such as segregating the data in question from view by the investigators, clinical team, or others as appropriate until the time of database lock and unblinding. In particular, data regarding

cortisol and other biomarkers will not be made available to the investigational team and the sponsor study team until after the database lock.

Under normal circumstances, the blind should not be broken until all subjects have completed the study and the database is finalized. Otherwise, the blind should be broken only if specific emergency treatment/course of action would be dictated by knowing the treatment status of the subject. In such cases, the investigator may in an emergency determine the identity of the treatment by contacting the IWRS. It is recommended that the investigator contact the sponsor or its designee if possible to discuss the particular situation, before breaking the blind. Telephone contact with the sponsor or its designee will be available 24 hours per day, 7 days per week. In the event the blind is broken, the sponsor must be informed as soon as possible. The date, time, and reason for the unblinding must be documented in the appropriate section of the CRF, and in the source document. The documentation received from the IWRS indicating the code break must be retained with the subject's source documents in a secure manner.

Subjects who have had their treatment assignment unblinded are required to return for an end-of-study visit.

## 6. DOSAGE AND ADMINISTRATION

JNJ-42847922 will be supplied for this study as 20-mg tablets. Quetiapine XR will be supplied as 50- and 150-mg tablets. In some instances, subjects will receive both active drug and a placebo capsule. All tablets will be over-encapsulated to ensure blinding.

All subjects will take 2 capsules daily. For subjects taking the lower dose, they will either take 1 capsule of 20-mg JNJ-42847922 or 150-mg quetiapine XR (after the first 2 days) along with 1 placebo capsule. For subjects taking the higher dose, they will take 2 capsules of either 20-mg JNJ-42847922 or 150-mg quetiapine XR. ([Table 2](#))

